5.1 Number of Digits to be Reported for Calculated Values

- 1) P values and statistics
Values will be rounded down to the third decimal place. However, P values less than 0.001 will be reported as “P < 0.001” or “< 0.001.”
- 2) Mean, standard deviation, standard error, adjusted mean, estimate of difference, and confidence interval
Values will be rounded off to one digit after the last place of the significant digits of the data.
- 3) Minimum, median, maximum, and quartiles
Values will be presented by the significant digits of the data.
- 4) Proportion, estimate and confidence interval of incidence
Values will be rounded off to the first decimal place.

5.2 Reporting of Prior and Concomitant Medications

Drug names will be reported according to the Iyakuhinmei Data File. Administration routes will be reported by code names (ROUTE) according to the CDISC SDTM Terminology.

5.3 Reporting of Complications, Adverse Events, and Adverse Drug Reactions

Primary SOCs and PTs will be reported according to the MedDRA.

5.4 Handling of Laboratory Test Values

Values below the limit of quantification will be handled as the value of the quantification limit.

5.5 Handling of Symptom Diary Data (NRS Score and Shiratori's Severity Criteria)

If the number of days of observation during the evaluation period is less than 4 days as of the time of calculation of the mean NRS score and the mean itch score based on the Shiratori's severity criteria at each time point, the score at that time point will be handled as missing.

5.6 Handling of Skindex-16 and 5-D Itch Scale Score

If the responses to the questions (components) used for calculation of the overall score or the subscores (symptoms score, emotions score, and functioning score) of the Skindex-16 or the total 5-D itch scale score are missing, the score will be handled as missing.

5.7 Time Windows for Assessment Time Points

Data for observations and tests will be handled according to the following criteria.

5.7.1 Handling of data in tabulation at each time point (excluding symptom diary

data)

- Data will be summarized by time point according to the time windows shown in [Table 5.7.1-1](#). Data obtained outside the time windows will be excluded from tabulation at each time point.
- If multiple data are available within the time window, the data obtained at scheduled visit will be employed.
- Data for observations and tests performed at unscheduled visits or 10 days after the day of the final dose will be excluded from the tabulation.
- For dependency assessment, all data collected will be employed regardless of the time window.

Table 5.7.1-1 Time windows for assessment time points

Assessment time point	Scheduled date ^{a)}	Time window
At Week -2	-14	Scheduled date \pm 3 days
At baseline	1	Day -3 to Day 1
At Weeks 1 to 12	$7 \times x + 1^b)$	Scheduled date \pm 3 days
At Weeks 18 to 58	$7 \times x + 1^b)$	Scheduled date \pm 7 days

a) The start of study treatment in the double-blind period is defined as Day 1 and the day before the start of study treatment as Day -1.

b) x: Number of weeks

5.7.2 Handling of data in tabulation at the final assessment point

- In the double-blind period, efficacy data (Skindex-16, 5-D itch scale, and PGIC) obtained at Weeks 1 to 4 (or at the time of withdrawal during the double-blind period before Week 4) and safety data obtained at Weeks 1 to 6 (or at the time of withdrawal during the double-blind period) will be included in the tabulation. Data for observations and tests performed at the latest time point within 10 days after the day of the final dose during the double-blind period will be used as the data at the end of the double-blind period. Data for observations and tests performed at unscheduled visits will be excluded from the tabulation.
- For the entire study period, data from Weeks 1 to 58 (or at the time of withdrawal during the extension period) will be included in the tabulation. Data for observations and tests performed at the latest time point within 10 days after the day of the final dose during the extension period will be used as the data at the end of the extension period. Data for observations and tests performed at unscheduled visits will be excluded from the tabulation.

6. Statistical/Analytical Issues**6.1 Adjustments for Covariates**

The change from baseline in the mean NRS score at Week 4 of the double-blind period, the primary variable, will be analyzed using the baseline mean NRS score and the presence of prior treatment with nalfurafine hydrochloride, a dynamic allocation factor, as a covariate. For details, refer to "[11.1.1 Primary variable](#)." If an imbalance is observed in the subject demographics of the FAS, the primary analysis set for efficacy, a supplementary analysis will be performed with

additional items showing the imbalance as the covariates in the primary analysis.

For the changes from baseline in the itch score based on the Shiratori's severity criteria, changes from baseline in Skindex-16, and changes from baseline in 5-D Itch Scale, an analysis will be performed using the baseline as a covariate for each item. Details are shown in "[11.2.1.1 Change from baseline in the mean itch score](#)," "[11.2.2.1 Changes from baseline in Skindex-16](#)," and "[11.2.3.1 Changes from baseline in 5-D itch scale](#)," respectively.

6.2 Handling of Dropouts or Missing Data

When there is a lack in the data used for analysis, all items, except for those listed in "[5 Handling of Data](#)" and below, will be handled as missing values, and no imputation by statistical methods will be performed.

- Sensitivity analyses of the primary variable will use multiple imputation. Details are shown in "[11.1.1.2 Sensitivity analysis](#)."

6.3 Interim Analyses and Data Monitoring

6.3.1 Interim analysis

When all data obtained in the double-blind period are locked, an interim analysis of the data in the double-blind period will be performed. The interim analysis will be performed on all analysis items except for those listed in "[12.6 Listing of Safety Variables](#)."

6.3.2 Interim tabulation

An interim tabulation will be performed at the time of application for approval of MR13A9, in order to attach the study results obtained up to that time. When data obtained up to Week 34 of the extension period, excluding dependency assessment data, are locked, a first interim tabulation of these data will be performed. The first interim tabulation will be performed on all analysis items except for dependency assessment data. When data obtained up to Week 34 of the extension period, including dependency assessment data, are locked, a second interim tabulation of these data will be performed. The second interim tabulation will be performed on all analysis items. Each interim tabulation will include data obtained up to Week 34.

For adverse events and adverse drug reactions, events occurring before the Week 34 visit will be included in the tabulation. For subjects who discontinued before Week 34 and entered the follow-up period, events occurring during the follow-up period will also be included in the tabulation. Information on the events collected by the time of interim tabulation will be used for tabulation.

For concomitant medications, those used prior to the Week 34 visit will be included in the tabulation.

6.4 Multicenter Study

Since the number of subjects per site is not large, analysis by site will not be performed.

6.5 Multiple Comparison and Multiplicity

6.5.1 Multiplicity of multiple analyses and multiple assessment time points

The interim analysis of the double-blind period is defined as the primary analysis, and Week 4 of the double-blind period is defined as the primary assessment time point. Since evaluations at other time points will be handled as references, multiplicity of multiple analyses and multiple assessment time points will not be adjusted.

6.5.2 Multiplicity among multiple items

Since the change from baseline in the mean NRS score at Week 4 of the double-blind period is handled as the primary variable, and other items are handled as references, multiplicity among multiple items will not be adjusted.

6.5.3 Multiplicity of multiple analysis sets

For the double-blind period, the FAS will be used as the primary analysis set for efficacy, and the PPS will be used for the supplemental analysis to examine the robustness of the results, so multiplicity among multiple analysis sets will not be adjusted. It is not applicable for safety because only the SS is used as the analysis set.

For the entire study period, it is not applicable for efficacy because only the FAS is used as the analysis set. It is not applicable for safety because only the SS is used as the analysis set.

6.6 Use of “Two Different Analysis Sets for Efficacy Evaluation” of Subjects

For the double-blind period, the primary efficacy analysis set will be the FAS. On the other hand, the analysis will also be performed in the PPS as a supplemental analysis to examine the robustness of the results. The definitions of FAS and PPS are detailed in “[2 Analysis Sets](#).”

6.7 Active-controlled Studies Intended to Show Non-inferiority

Not applicable.

6.8 Examination of Subgroups

As the subgroup analyses of efficacy endpoints, the matters shown in “[11.3 Efficacy Subgroups](#)” will be performed. As the subgroup analyses of safety endpoints, the matters shown in “[12.5 Safety Subgroups](#)” will be performed.

7. Definition of Derived Data

Each variable will be calculated using the following formula:

- Disease duration of itch (years) = Date of written informed consent (year) – Time of onset of itching (year)
- Hemodialysis history (years) = Date of written informed consent (year) – Date of initiation of hemodialysis (year)
- Urea reduction ratio at baseline (%) = $([\text{BUN before dialysis} - \text{BUN after dialysis}] / \text{BUN before dialysis}) \times 100$

- Treatment compliance (%) = Number of doses of the study drug / Number of dialysis sessions performed during the double-blind and extension periods $\times 100$
- Treatment duration (days) = Day of the final dose – Start of the study treatment + 1
- Average dose per dry weight ($\mu\text{g}/\text{kg}$) = Total dose of the study drug per dry weight / Number of doses
- NRS score and itch score based on Shiratori's severity criteria
 - Mean score at each time point = Sum of scores observed during the assessment time window / Number of days when the score was observed during the assessment time window
 - *The details of the assessment time window are shown in [Table 11.1-1](#) and [Table 11.1-2](#).
 - Change from baseline in the mean score at each time point = Mean score at each time point – Mean score at baseline
 - Change from baseline in daily score = Daily score – Mean score at baseline
- Skindex-16¹⁾
 - Score for each question = Response for each question / 6 $\times 100$
 - Total score = Sum of scores for all questions / 16
 - Subscores
 - Symptoms score = (Sum of scores for Questions 1 to 4) / 4
 - Emotions score = (Sum of scores for Questions 5 to 11) / 7
 - Functioning score = (Sum of scores for Questions 12 to 16) / 5
- 5-D itch scale
 - The total score will be calculated as the sum of scores for the following questions (components)²⁾:
 - (1) Duration: 1 to 5 points
 - (2) Degree: 1 to 5 points
 - (3) Direction: 1 to 5 points
 - (4) Disability: 1 to 5 points
 - The highest score among sleep, leisure/social, housework/errands, and work/school will be used.
 - (5) Distribution: 1 to 5 points
 - The score is determined according to the total number of body parts with itching as follows:
 - 0 to 2: 1 point
 - 3 to 5: 2 points
 - 6 to 10: 3 points
 - 11 to 13: 4 points

- 14 to 16: 5 points
- Time to onset of an adverse event (days) = Date of onset of the adverse event – Start of study treatment + 1

8. Disposition of Subjects

Analysis for the double-blind period will include subjects who entered the double-blind period. Analysis for the entire study period will include subjects who entered the extension period.

8.1 Analysis set

The number and percentage of subjects who were included or excluded in the FAS, PPS (only for the double-blind period), and SS will be presented. For the double-blind period, the between-group imbalance will be examined by Fisher's exact test.

8.2 Presence or Absence and Reasons of Discontinuation

The number and percentage of subjects for presence or absence of discontinuation will be presented. For the double-blind period, the between-group imbalance will be examined by Fisher's exact test. Reasons for discontinuation will be classified into the following categories, and the number and percentage of subjects will be presented for each category.

- Adverse event: When the discontinuation is due to discontinuation criteria (discontinuation of individual subjects) 1) "adverse events"
- Lack of efficacy: When the discontinuation is due to discontinuation criteria (discontinuation of individual subjects) 2) "lack of efficacy"
- Withdrawal by subject: When the discontinuation is due to discontinuation criteria (discontinuation of individual subjects) 3) "voluntary request for study discontinuation by the subject"
- Significant deviation: When the discontinuation is due to discontinuation criteria (discontinuation of individual subjects) 4) "significant deviation from the protocol during the study"
- Other: When the reason for discontinuation does not fall under the categories of "adverse events," "lack of efficacy," "voluntary request for study discontinuation by the subject," or "significant deviation."

9. Demographic and Other Baseline Characteristics

9.1 Subject Demographics

Analysis items are shown below. If there are data at more than one time point, the data at baseline will be used for evaluation.

- Nominal scale variables
 - Sex: Male, female
 - Primary disease of dialysis: Diabetic nephropathy, glomerulonephritis chronic, nephrosclerosis, polycystic kidney, pyelonephritis chronic, other, unspecified

- Type of dialysis: HD, off-line HDF, on-line HDF, I-HDF
- Remaining renal function: No, yes
- Prior treatment with nalfurafine hydrochloride: No, yes
- Specific signs or symptoms occurring during the screening period*: No, yes
 - *Specific signs or symptoms: Dizziness, syncope, palpitations, tachycardia, fall, seizure, gait disturbance, mental status changes, somnolence, mood changes
- Ordinal scale variables
 - Age: < 65 years, ≥ 65 years
 - Dry weight at the start of the screening period: < 45 kg, ≥ 45 and < 65 kg, ≥ 65 and < 85 kg, ≥ 85 kg
 - Mean NRS score: < 6, ≥ 6
- Continuous variables: Age, dry weight at the start of the screening period, hemodialysis history, single-pool Kt/V, urea reduction ratio, disease duration of itch, mean NRS score, mean itch score based on the Shiratori's severity criteria (higher of daytime or night-time), Skindex-16 (overall score), 5-D Itch Scale (total score)

The number and percentage of subjects for nominal and ordinal scale variables, and summary statistics for continuous variables will be presented for the overall population and by group. However, only the number of subjects is shown for the primary disease of dialysis.

For the double-blind period, the between-group imbalance will be examined by tests for the prior treatment with nalfurafine hydrochloride, dry weight at the start of the screening period (ordinal scale variable), and mean NRS score (continuous variable). Depending on the characteristics of the data, Fisher's exact test will be used for nominal scale variables, two-sample Wilcoxon test for ordinal scale variables, and two-sample t-test for continuous variables.

9.2 Complications

The numbers and percentages of subjects are presented for all complications and by primary SOC and PT.

9.3 Concomitant Medications for Target Disease (Itching)

The numbers and percentages of subjects will be presented by generic name and route of administration.

The medications used during the following periods will be tabulated:

- Double-blind period: From the start of study treatment to the end of the double-blind period
- Entire study period: From the start of study treatment to the end of the extension period

9.4 Medications Used to Treat Complications

The numbers and percentages of subjects will be presented by generic name and route of administration.

The medications used during the following periods will be tabulated:

- Double-blind period: From the start of study treatment to the end of the double-blind period
- Entire study period: From the start of study treatment to the end of the extension period

10. Treatment Compliance

10.1 Number of Doses

The number of doses of the study drug will be classified into the following categories (unit: doses), and the number and percentage of subjects will be presented for each category.

- Double-blind period: ≤ 3 , $4 \leq \leq 6$, $7 \leq \leq 9$, $10 \leq \leq 12$, $13 \leq \leq 15$, $16 \leq \leq 18$, $19 \leq$
- Entire study period: ≤ 36 , $37 \leq \leq 72$, $73 \leq \leq 108$, $109 \leq \leq 144$, $145 \leq \leq 180$, $181 \leq$

10.2 Treatment Compliance

Summary statistics will be presented.

10.3 Treatment Duration

Summary statistics will be presented.

10.4 Average Dose per Dry Weight

Summary statistics will be presented.

The assessment periods are as follows:

- Double-blind period: Overall
- Entire study period
 - MR-MR group: Weeks 1 to 6, Weeks 7 to 58, overall
 - P-MR group: Weeks 1 to 6, Weeks 7 to 58

10.5 Change in Dry Weight Category

The status of change in the dry weight category (< 45 kg, ≥ 45 and < 65 kg, ≥ 65 and < 85 kg, ≥ 85 kg) at the time of determination of the study drug dose will be classified into the following categories, and the number and percentage of subjects will be presented for each category. Subjects falling under the dose increase and decrease category will only be presented for overall of the entire study period.

- No change: Subjects with no change in category
- Dose increase: Subjects whose dry weight increased, resulting in category change (excluding those in the dose increase and decrease category)
- Dose decrease: Subjects whose dry weight decreased, resulting in category change (excluding those in the dose increase and decrease category)
- Dose increase and decrease: Subjects whose dry weight increased and decreased, resulting

in category change

The assessment periods are as follows:

- Entire study period
 - Weeks 7 to 34: Status of change from the time of determination of study drug dose for Weeks 1 to 6 (start of the screening period)
 - Weeks 35 to 58: Status of change from the time of determination of study drug dose for Weeks 7 to 34 (Week 6)
 - Overall: Status of change from the time of determination of study drug dose for Weeks 1 to 6 (start of the screening period)

11. Efficacy

11.1 Primary Endpoint

The primary endpoint is the NRS score. Assessment time points and their time windows in the screening period, the double-blind period, and the extension period are shown in [Table 11.1-1](#). The assessment time point and its time window in the follow-up period are shown in [Table 11.1-2](#).

Table 11.1-1

Assessment time points and their time windows in the screening period, the double-blind period, and the extension period

Period	Assessment time point	Time window ^{a)}
Screening period	At Week -1	From Day -13 to Day -7
Double-blind period	At baseline	From Day -6 to Day 1
	At Weeks 1 to 6	From Day $7 \times x - 5$ to Day $7 \times x + 1$ ^{b)}
Extension period	At Weeks 7 to 58	From Day $7 \times x - 5$ to Day $7 \times x + 1$ ^{b)}

a) The start date of the double-blind period will be regarded as Day 1 and the previous day of the start date of the double-blind period will be regarded as Day -1.

b) x: Number of weeks

Table 11.1-2

Assessment time point and its time window in the follow-up period

Period	Assessment time point	Time window ^{a)}
Follow-up period	At Week 1	From Day 1 to Day 7

a) The start date of the follow-up period (the completion date of the extension period or the next day of the date of discontinuation) will be regarded as Day 1.

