### **5.3.2 Responses to the discontinuation of any individual subject**

- If a subject meets any of the criteria described in “[5.3.1 Discontinuation criteria \(discontinuation of individual subjects\)](#)” during the study, the principal investigator or subinvestigator will immediately decide to discontinue the study. On the next dialysis day after the decision to discontinue, the prespecified assessment items at discontinuation will be measured and assessed and the date of discontinuation and the reason for discontinuation will be recorded in the case report form. The date of discontinuation will be the day when the principal investigator or subinvestigator decides to discontinue the study. If the study is discontinued during the double-blind period or the extension period, the next day of the assessments at discontinuation will be regarded as the start date of the follow-up period.
- If the study is discontinued because of the occurrence of an adverse event, the principal investigator or subinvestigator will promptly provide appropriate treatment for the subject and perform a follow-up investigation, as instructed in “[10.13.9 Follow-up investigation](#).”
- If a subject does not return to the study site, the principal investigator, subinvestigator, or clinical research coordinator will immediately investigate the reason for missed visits and the subsequent course.

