### **10.6 Efficacy Endpoints**

#### **10.6.1 Symptom diary (electronic diary)**

The principal investigator, subinvestigator, or clinical research coordinator will instruct each subject on how to record the symptom diary, as well as register the information on each subject in the electronic diary system to prepare for the start of recording.

1) NRS score

Looking back on the period between the time of awakening on the previous day of assessment and the time of awakening on the day of assessment (including sleeping hours) once daily, subjects will assess the NRS score for the most severe itching by themselves and record the score in the symptom diary. According to [Appendix 1](#), the most severe itching within the day will be recorded in integers on a scale ranging from 0 to 10, where 0 represents no itching and 10 represents worst itching imaginable.

2) Shiratori's severity criteria

Looking back on the period between the time of awakening on the previous day of assessment and the time of awakening on the day of assessment (including sleeping hours) once daily, subjects will assess the degree of itching by themselves and record the score in the symptom diary. According to [Appendix 2](#), the symptoms during the day and the night will be recorded on a scale ranging from 0 to 4, where 0 represents no symptoms and 4 represents severe itching.

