### **11.16 Visit 15 (Week 58, at the Start of the Follow-up Period)**

- Review of the symptom diary

- Confirmation of adverse events, concomitant medications, and concomitant therapies
- Dependency assessment (before dialysis)
- Confirmation of the implementation status of hemodialysis
- Skindex-16
- 5-D itch scale
- PGIC
- Body weight (before dialysis)
- 12-lead ECG
- Vital signs
- Laboratory tests (hematology, blood biochemistry, endocrinology)
- Pregnancy test (only in women of childbearing potential)
- Confirmation of the compliance with study treatment

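### The follow-up Week 1 diary window opens on a day that nominally already belongs to Week 58 and, for subjects who withdraw during the extension, 1 to 3 days before the protocol's own start of follow-up

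*SAP*

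**What the plan says.** SAP 11.1 assigns diary days to weekly windows. Baseline is "From Day -6 to Day 1", and Week x, for x from 1 to 58, runs from Day 7x − 5 to Day 7x + 1. Follow-up Week 1 is "From Day 1 to Day 7" on a separate count. Footnote a to Table 11.1-2 puts Day 1 of that count at the start of follow-up, which it gives as "the completion date of the extension period or the next day of the date of discontinuation". Protocol 14.5.1 (Table 14.5.1-2) carries the same footnote.

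Elsewhere the protocol describes the start of follow-up as follows:

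- Section 11.16 labels the Week 58 visit (Visit 15) as the start of follow-up. The study schedule allows that visit in Weeks 57–59.
- Section 5.3.2 covers withdrawals: "The date of discontinuation will be the day when the principal investigator or subinvestigator decides to discontinue the study". The assessments at discontinuation take place on the next dialysis day, and "the next day of the assessments at discontinuation will be regarded as the start date of the follow-up period".
- Section 8.2.4 and the synopsis define follow-up as the week after those assessments or after the end of the extension.

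Under protocol 10.6.1, each diary score covers the time between "the time of awakening on the previous day of assessment and the time of awakening on the day of assessment".

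**The concern.** The weekly windows follow one convention: the first day of a new period closes the previous window. Day 1 belongs to baseline and Week 1 starts on Day 2. Day 43, the start of the extension, belongs to Week 6, and Week 7 starts on Day 44. This suits a diary that looks back to the previous morning. The follow-up window breaks the convention by taking its opening day from the period just ended.

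For withdrawals there is also a plain contradiction. The footnote and protocol 5.3.2 both claim to give the start date of follow-up, and they give different days.

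At stake is the one planned measure of itch after treatment ends. Protocol 11.17 lists no Skindex-16, 5-D itch scale or PGIC at the final visit, and the SAP's time points for those scales stop at Week 58. The diary mean for follow-up Week 1 is therefore the only efficacy summary that could show itch returning.

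**Working it through.** **Completers, nominal schedule**

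- Week 58: 7 × 58 − 5 = 401 and 7 × 58 + 1 = 407, so Days 401–407.
- The Week 58 visit is nominally Day 407. Taking it as the completion date, follow-up Week 1 is Days 407 to 407 + 6 = 413.
- Shared day: 407. Its entry describes Day 406 to Day 407, which is before follow-up starts.
- Day 414, the nominal Week 59 visit day, is in no window.
- Continuing the weekly rule to x = 59 gives 7 × 59 − 5 = 408 to 7 × 59 + 1 = 414, with no overlap.
- If completion is instead read as the last day of the 52 weeks (43 + 52 × 7 − 1 = 406), follow-up Week 1 is Days 406–412 and two days, 406 and 407, are shared.

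**Completers, using the Visit 15 allowance**

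The Week 58 window is fixed from the first dose, while the follow-up window moves with the subject. With the visit on the same weekday as the first dose:

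| Visit 15 | Completion date | Follow-up window | Days shared with Week 58 |
|---|---|---|---|
| Week 57 | 400 | 400–406 | 6 (401–406); Day 400 is shared with Week 57 |
| Week 58 | 407 | 407–413 | 1 (407) |
| Week 59 | 414 | 414–420 | 0 |

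**Extension withdrawals**

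Let D be the decision day and g the number of days to the next dialysis session.

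- Footnote window: D + 1 to D + 7.
- Protocol 5.3.2: assessments on D + g, so follow-up is D + g + 1 to D + g + 7.
- Days in common: D + g + 1 to D + 7, which is 7 − g days.

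The documents do not fix the dialysis weekdays. Assuming Monday/Wednesday/Friday or Tuesday/Thursday/Saturday:

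| Decision day | Mon | Tue | Wed | Thu | Fri | Sat | Sun |
|---|---|---|---|---|---|---|---|
| g, Mon/Wed/Fri | 2 | 1 | 2 | 1 | 3 | 2 | 1 |
| g, Tue/Thu/Sat | 1 | 2 | 1 | 2 | 1 | 3 | 2 |

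So g is 1 to 3, and 4 to 6 of the seven footnote days lie in the protocol's follow-up week.

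**Size, by illustration**

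Suppose itch returns by a constant d from the Day 408 entry onward and the schedule is nominal. The mean over Days 407–413 then shows a return of (0 + 6d)/7 = 6d/7 ≈ 0.857d, which is 14.3% low. The mean over Days 408–414 shows 7d/7 = d.

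**Where the window is used**

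SAP 11.1.2.1 to 11.1.2.3, 11.2.1.1, 11.2.1.2 and 11.2.1.5 include follow-up Week 1 in the entire-study results. These give summary statistics, within-group one-sample t-tests and responder percentages. The two-sample t-tests and Fisher tests in those sections apply to the double-blind period, whose time points end at Week 6.

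**The case against.** The strongest reply is that little depends on this window. SAP 6.5 makes Week 4 the primary time point and treats other time points and items as references. No between-group comparison uses follow-up Week 1, and conclusions on superiority do not rest on it. That stands, and it limits the point to a minor correction.

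For completers the footnote also has support: protocol 11.16 calls the Week 58 visit the start of follow-up. That explains how the rule arose, but it does not prevent the double count.

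A reader might infer several stronger points, which the documents do not support:

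- *Exactly one day is double-counted for every completer.* The Visit 15 allowance makes the overlap anything from 0 to 6 days of Week 58.
- *The SAP departs from the protocol.* Protocol 14.5.1 carries the same footnote. The protocol is inconsistent with itself, and the SAP repeats it.
- *For withdrawals, the early start mixes in treated days.* The discontinuation schedule shows no study treatment at that visit, so the days between decision and assessments are ordinarily off drug. A subject withdrawn for seven consecutive missed doses has already gone about 7 ÷ 3 ≈ 2.3 weeks without one.
- *All withdrawals are affected.* The entire-study groups (protocol 14.2.2, SAP Table 3-2) include only subjects who entered the extension, so double-blind withdrawals never reach this summary.
- *The result is purely descriptive.* The one-sample t-tests at follow-up Week 1 do use the window.

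**Conclusion.** The footnote is wrong as written, with small consequences. On the nominal schedule it counts Day 407 twice and omits Day 414. For extension withdrawals it contradicts protocol 5.3.2 and 8.2.4 by 1 to 3 days, given regular thrice-weekly dialysis. The 6/7 figure is an illustration that rests on nominal timing and an immediate, uniform return of itch. The documents give no post-treatment course from which to estimate the actual bias. For withdrawals the definitions conflict, but no direction of bias is shown.

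**What to change.** In the footnotes to both tables, define follow-up Day 1 as:

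- for completers, the day after the subject's actual extension completion date, stating that this is the date of the Week 58 visit (nominally giving Days 408–414);
- for extension withdrawals, the day after the assessments at discontinuation, as in protocol 5.3.2.

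Add that a diary day assigned to follow-up is not counted in any treatment-week window. The new start date alone is not enough. With Visit 15 on Day 400, follow-up becomes Days 401–407, which is the whole Week 58 window. With the added sentence, such a subject has no Week 58 diary days, so that mean is missing under the existing four-day minimum. The number of such subjects should be reported.

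The cost is a revised footnote and one sentence in each document. No new data are needed, because diary entries continue to the end of follow-up. Any follow-up Week 1 and late treatment-week tables already produced would need to be rerun.
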